5 METHODOLOGY

5.1 Entry Criteria

5.1.1 *Diagnosis/Condition for Entry into the Trial*

The study will be conducted in male subjects with histologically confirmed mCRPC who have progressed or become resistant to no more than 2 prior systemic treatment regimens with chemotherapy, targeted therapies, radiopharmaceuticals, or immunotherapy in the metastatic setting. Hormonal treatment will not be considered when determining the number of prior regimens in the metastatic setting. Subjects cannot have had more than 1 prior chemotherapeutic regimen in the metastatic setting. Subjects with evidence of progressive bone or other metastases are acceptable. Subjects may remain on castration therapy (luteinizing-hormone-releasing hormone [LHRH] agonist or antagonist) during the trial.

5.1.2 *Subject Inclusion Criteria*

In order to be eligible for participation in this trial, the subject must:

1. Be willing and able to provide written informed consent for the trial.
2. Be ≥ 18 years of age on day of signing informed consent.
3. Have progressive metastatic castration resistant prostate cancer, on androgen deprivation therapy, based on at least one of the following criteria:
 - a. PSA progression defined as 25% increase over baseline value with an increase in the absolute value of at least 2 ng/mL that is confirmed by another PSA level with a minimum of a 1-week interval with a minimum PSA of 2 ng/ml.
 - b. Progression of bi-dimensionally measurable soft tissue (nodal metastasis) assessed within 1 month prior to registration by a CT scan or MRI of the abdomen and pelvis (please refer to [Section 7.1.2.5.1](#) for definitions of measurable disease).

- c. Progression of bone disease (evaluable disease) (new bone lesion(s)) by bone scan. (Please refer to [Section 7.1.2.5.1](#) for definitions of evaluable disease).
4. Has discontinued antiandrogens (bicalutamide, nilutamide) >6 weeks and enzalutamide or abiraterone >4 weeks prior to Day 1 of trial treatment
5. Have a performance status of 0 or 1 on the ECOG Performance Scale.
6. Demonstrate adequate organ function as defined in [Table 3](#). All screening labs should be performed within 28 days of treatment initiation.

Table 3 Adequate Organ Function Laboratory Values

System	Laboratory Value
Hematologic	
Absolute neutrophil count (ANC) ^a	≥1000 /mcL
Platelets ^a	≥75,000 / mcL
Hemoglobin ^a	≥9 g/dL or ≥5.6 mmol/L
Lymphocytes	≥500 / mcL
Renal	

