7.1.2.4 *Eastern Cooperative Oncology Group (ECOG) Performance Scale*

The Investigator or qualified designee will assess ECOG status (see [Section 12.1](#)) at screening, prior to the administration of each dose of trial treatment and discontinuation of trial treatment as specified in the Trial Flow Chart ([Section 6](#)).

7.1.2.6 *Tumor Imaging and Assessment of Disease*

Computed tomography (CT), magnetic resonance imaging (MRI) or bone scan will be considered the best currently available and reproducible methods to measure target lesions (as defined in [Section 7.1.2.5.2](#)) selected for response assessment. Conventional CT and MRI of the abdomen/pelvis should be performed with contiguous cuts of 10 mm or less. Spiral CT scan should be performed using a 5 mm contiguous reconstruction algorithm (as a general rule, lesion diameter should be no less than double the slice thickness). Lesions on chest x-rays will be acceptable as measurable lesions when they are clearly defined and surrounded by aerated lung; however, CT is preferable.

Ultrasound will not be an acceptable method to measure disease. Bone scan response assessment will be primarily based on the PCWG2 criteria. [\[38\]](#)

7.1.2.6.1 *Measurable and Non-measurable Lesions and Disease*

Measurable lesions will be those that can be accurately measured in at least one dimension with the longest diameter ≥ 10 mm (for spiral CT scan or MRI scan, ≥ 5 mm). Measurable disease will be present if the subject has 1 or more measurable lesions.

Non-measurable lesions/disease will be all other lesions (or sites of disease), including small lesions (those with all measurements <10 mm with spiral CT or <5 mm with MRI), or any of the following: bone lesions, leptomeningeal disease, ascites, pleural or pericardial effusion, lymphangitis, cutis/pulmonis, abdominal masses that are not confirmed and followed by imaging techniques, cystic lesions, and lesions occurring within a previously irradiated area unless they are documented as new lesions since the completion of radiation therapy.

7.1.2.6.2 *Target/Non-Target Lesions*

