7.1.2.6.3 Response in Measurable Lesions (RECIST 1.1)

At baseline, the sum of the longest diameters (SumD) of all target lesions (up to 2 lesions per organ, up to total 5 lesions) is measured. At each subsequent tumor assessment (TA), the SumD of the target lesions and of new, measurable lesions are added together to provide the total measurable tumor burden (TMTB):

TMTB = SumD target lesions + SumD new, measurable lesions

Percentage changes in TMTB per assessment time point describe the size and growth kinetics of both old and new measurable lesions as they appear. At each TA, the response in target and new measurable lesions is defined based on the change in TMTB (after ruling out irPD) as follows:

- Complete Response (CR): disappearance of all target lesions. Any pathological lymph nodes (whether target or non-target) must have reduction in short axis to ≤ 10 mm.
- Partial Response (PR): At least a 30% decrease in sum of diameter of target lesions, taking as reference the baseline sum diameter.
- Stable Disease (SD): Neither sufficient shrinkage to qualify for PR nor sufficient increase to qualify for PD, taking as reference the smallest sum diameters while on study.
- Progressive Disease (PD): At least a 20% increase in the sum of diameters of target lesions, taking as reference the smallest sum on study (this includes the baseline sum if that is the smallest on study). In addition to the relative increase of 20%, the sum must also demonstrate an absolute increase of at least 5 mm. (Note: the appearance of one or more new lesions is also considered progression).

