Time to progression will be defined as the time from the first day of treatment until the date progressive disease or death is first reported. Subjects who die without a reported prior progression will be considered to have progressed on the day of their death. Subjects who did not progress will be censored at the day of their last tumor assessment.

Tumor response rate is the total number of CRs plus PRs divided by the number of treated subjects. Disease control rate is the number of subjects who have CR+PR+SD for a minimum of 12 weeks following the first day of treatment, divided by the number of response-evaluable subjects.

[REDACTED]

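### The tumor response rate divides CR+PR by all treated subjects, although subjects with only non-measurable disease may enter and cannot reach PR, so the rate depends on an unknown case mix

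*Combined protocol and SAP*

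**What the plan says.** **Entry.** Inclusion criterion 3 (Section 5.1.2) reads "Have progressive metastatic castration resistant prostate cancer, on androgen deprivation therapy, based on at least one of the following criteria". One route is "PSA progression defined as 25% increase over baseline value with an increase in the absolute value of at least 2 ng/mL", with confirmation. Another is "Progression of bone disease (evaluable disease) (new bone lesion(s)) by bone scan". Only the nodal soft-tissue route refers to measurable disease, and no visible criterion requires a measurable lesion.

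**Measurability.** Section 7.1.2.6.1 treats bone disease as non-measurable; its list reads in part "or any of the following: bone lesions, leptomeningeal disease, ascites". On size, the same paragraph also places in this group "small lesions (those with all measurements <10 mm with spiral CT or <5 mm with MRI". Section 7.1.2.6.5 gives guidance for a subject whose disease is entirely non-measurable.

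**Response.** PR under RECIST 1.1 (Section 7.1.2.6.3) is "At least a 30% decrease in sum of diameter of target lesions, taking as reference the baseline sum diameter". irPR (Section 7.1.2.6.4) is a fall of at least 30% in total measurable tumor burden relative to baseline. For non-target disease, Section 7.1.2.6.5 offers CR, non-CR/non-PD and PD.

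**Denominators.** Section 8.2.4 uses treated subjects for the response rate: "Tumor response rate is the total number of CRs plus PRs divided by the number of treated subjects". For disease control it uses a count "divided by the number of response-evaluable subjects", a term that the visible text does not define. Section 8.2.1 places in the efficacy analyses those who complete at least one cycle.

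**Purpose.** Section 3.2 says that the activity estimate is to inform a later randomized Phase 2 design.

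**The concern.** A response rate used for planning should describe activity in subjects who could show the response. Here the denominator includes an unspecified number who cannot reach PR whatever the drug does. Their share is not limited by eligibility or by stratification (Section 5.4), and it is not among the visible baseline summaries. A reader of the results could not separate low activity from a large share of subjects with only non-measurable disease, and could not carry the rate to a trial with a different mix. The three differing denominators add to the ambiguity.

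A related but separate problem lies in the measurability definition. Its two paragraphs disagree on small spiral-CT lesions, and that decides who has a target lesion at all.

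**Working it through.** **1. The plan's own figures.** No target response rate, power or precision is stated, and Section 8.1 excludes inferential analysis. The only figure to reproduce is the total of about 51. Up to 21 in Part A (Section 2.1.1) plus about 30 at the Part B RP2D (Section 5.2.1.1.3) gives 21 + 30 = 51. The sum is an inference, since the documents do not show it. It supplies n of about 30 for the illustration.

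**2. Which responses remain open without a target lesion.**
- PR and irPR need a 30% fall from a baseline sum. With no target lesion that sum is zero, so neither can be met.
- Table 13 also gives PR for a target-lesion CR with residual or unevaluated non-target disease, but that presupposes a target lesion.
- CR stays possible through disappearance of all non-target lesions (with marker normalization under RECIST 1.1).
- In Tables 13 and 14, the rows marked Any for target lesions already assign PD or irPD from non-target progression or new lesions. The CR and non-CR/non-PD outcomes have no row. If a programmer coded the empty target set as CR, persisting non-target disease would read as PR, which would push the rate upward.

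**3. Formula.** Let m be the share with measurable disease, r the CR+PR rate among them, and c the CR rate among the rest.

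All-treated rate = m × r + (1 − m) × c

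None of m, r or c is in the documents; all are assumed.

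| m | r | c | All-treated rate |
|---|---|---|---|
| 0.40 | 20% | 0 | 0.40 × 0.20 = 8% |
| 0.70 | 20% | 0 | 0.70 × 0.20 = 14% |
| 0.30 | 20% | 0 | 6% |
| 0.80 | 20% | 0 | 16% |
| 0.30 | 20% | 5% | 0.06 + 0.70 × 0.05 = 9.5% |
| 0.80 | 20% | 5% | 0.16 + 0.20 × 0.05 = 17% |

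At n = 30, m of 0.40 to 0.70 means that 12 to 21 subjects could contribute a PR and 18 to 9 could not.

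**4. Sampling error.** At n = 30, 8% is 2.4 responders and 14% is 4.2. Exact (Clopper-Pearson) 95% intervals:
- 2/30 = 6.7% (0.8% to 22.1%)
- 4/30 = 13.3% (3.8% to 30.7%)
- 2/12 = 16.7% (2.1% to 48.4%)
- 4/21 = 19.0% (5.4% to 41.9%)

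The intervals are wider than the 8-14% spread, and the measurable-disease denominator widens them further.

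**5. Denominators side by side.** A treated subject who stops during cycle 1 counts in the response rate of Section 8.2.4 but falls outside the efficacy set of Section 8.2.1. Whether that subject counts for disease control cannot be told, because response-evaluable is undefined. None of the three is limited to measurable disease in the visible text.

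**6. The size threshold.** Section 7.1.2.6.1 first sets measurability at 5 mm or more for spiral CT or MRI. Its second paragraph makes anything below 10 mm on spiral CT non-measurable. A 5-9 mm spiral-CT lesion is therefore both. Section 7.1.2.6 asks that a lesion be at least twice the slice thickness, and 2 × 5 mm = 10 mm. Sections 7.1.2.6.4 and 7.1.2.6.6 and Table 12 use 10 mm for new lesions. On a single 6 mm target lesion, 20% growth is 0.20 × 6 = 1.2 mm and a 30% fall is 0.30 × 6 = 1.8 mm. RECIST 1.1 PD also needs a 5 mm absolute increase; irPD has no such floor.

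**The case against.** An all-treated denominator is clear and conservative, and it prevents exclusions chosen after the fact. The trial is descriptive and activity is a secondary objective, so no error rate is at risk. Target lesions are recorded at baseline (Section 7.1.2.6.2), so a measurable-disease rate could be derived later without loss of data. These points stand. They are reasons to keep the all-treated line, but they do not make it sufficient alone.

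The plan is not silent on non-measurable disease. Section 7.1.2.6.5 supplies response categories, bone-scan response rests mainly on PCWG2 (Section 7.1.2.6), and Section 8.1 adds PSA change and survival. That also stands: what is missing is a separate tabulation and a rule for the response rate. PCWG2 leaves the denominator unchanged, and the visible text does not say which criteria apply to which subjects.

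A reader might infer that these subjects contribute nothing to the numerator. The documents do not support that, because a non-target CR counts. A reader might also infer a distorted contrast between Parts A and B. No such comparison is planned: allocation is non-random, there is no inference, and exclusion 13 does not apply to Part A, so the populations may differ anyway.

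On small lesions, early irPD generally needs a confirmatory scan, target lesions are selected by size and suitability for repeated measurement, and a lone 6 mm target is a worst case. The false-progression concern is therefore limited mainly to irRECIST.

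Some baseline and efficacy items are redacted and could include measurable-disease status or a definition of response-evaluable.

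**Conclusion.** The point holds in limited form. On the visible text, the planned tumor response rate mixes activity with the share of subjects who have measurable disease, and nothing visible fixes or reports that share. The 8-14% illustration assumes 40-70% measurable, a 20% rate among them and no CRs in the rest. It should not be read as an estimate of bias in this trial: the share is unknown, entry on PSA or bone progression does not show that a subject lacks measurable lesions, and sampling error at about 30 subjects exceeds the spread.

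Two items are inconsistent as written whatever the case mix. The efficacy denominators in Sections 8.2.1 and 8.2.4 disagree, with response-evaluable undefined, and the spiral-CT threshold in Section 7.1.2.6.1 contradicts itself.

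**What to change.** - **Section 8.2.4:** report CR+PR by RECIST 1.1 and by irRECIST, by Part, among treated subjects with at least one measurable lesion at baseline. Count unassessed subjects in that group as non-responders. Keep the all-treated rate beside it.
- **Baseline summaries:** tabulate measurable-disease status.
- **Subjects with only non-measurable disease:** report them separately with the categories of Section 7.1.2.6.5, and PCWG2 for bone. Add the missing CR and non-CR/non-PD rows to Tables 13 and 14; PD needs no new row.
- **Denominators:** define response-evaluable, and reconcile completion of at least one cycle (Section 8.2.1) with treated subjects (Section 8.2.4).
- **Section 7.1.2.6.1, as a separate correction:** set one spiral-CT threshold consistent with the double-slice rule and the 10 mm used elsewhere, and state whether MRI follows it.

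The cost is wording, a baseline row and one table, with no added subjects or scans. The downside is a smaller denominator and a wider interval for the measurable-disease line.

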2.1.2 Part B – ADXS31-142 + Pembrolizumab (MK-3475) Combination Therapy

Part B of the study will be an open-label, Phase 1-2, multicenter, non-randomized dose-determining trial of ADXS31-142 in combination with pembrolizumab (MK-3475) in subjects with mCRPC. Part B will consist of a dose-determination phase followed by an expansion cohort phase. The dose-determination phase is intended to select a RP2D for the combination. A modified 3+3 design will be used to determine the dose of ADXS31-142 in combination with pembrolizumab (MK-3475).

[figure not shown]
During the dose-determining stage, subjects will be entered at a dose of 1×10^9 of ADXS31-142 (see [Table 7](#)) in combination with pembrolizumab (MK-3475) at 200 mg. If this dose combination is not tolerable, then Dose Level -1 at a dose of 0.5×10^9 of ADXS31-142 in combination with pembrolizumab (MK-3475) at a dose of 200 mg will be evaluated. Dose-determination will continue until identification of a recommended RP2D for the combination to be used in the expansion cohort. A minimum of 6 subjects will be treated at the RP2D before initiating the expansion cohort.

The expansion cohort will be open for enrollment once the RP2D of ADXS31-142 in combination with pembrolizumab (MK-3475) is selected in the Part B dose-determination phase. Further assessment of the RP2D will be explored in up to 30 subjects with mCRPC to evaluate the safety and clinical activity of ADXS31-142 in combination with pembrolizumab (MK-3475).

Adverse events will be monitored from the time informed consent is obtained and graded in severity according to the guidelines outlined in the National Cancer Institute (NCI) Common Terminology Criteria for Adverse Events (CTCAE) Version (v) 4.03.

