5.10 Subject Replacement Strategy

Subjects will not be replaced.

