Tumor Imaging/Disease Assessment - CT scan, MRI or bone scan for determination of unidimensional measurements and disease response. Baseline tumor imaging/disease assessment must be performed within 28 days prior to the first dose of ADXS31-142 and at Week 10 (\pm 1 week) for the first cycle and then every 12 weeks (\pm 1 week). Imaging areas will include the chest, abdomen, pelvis, and other areas as indicated by clinical presentation.

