8.2 Statistical Analysis Plan

8.2.1 Analysis Sets

The safety population will include all subjects who have been treated with at least one dose of ADXS31-142 or pembrolizumab (MK-3475).

All subjects who complete at least one cycle of study treatment will be included in the efficacy analyses. Characterization of the Study Population

Distributions of the following baseline data will be described by dose group:

- Demographics
- AJCC TNM prostate cancer stage
- Prior treatments and regimen for prostate cancer
- ECOG Performance Status
- Physical examination parameters

- Vital signs
- Baseline safety labs including hematology and serum chemistry
- Baseline immunology data
- [REDACTED]
- [REDACTED]

8.2.2 *Study Conduct*

Information about study conduct will be presented by treatment dose. Subject disposition at the end of the study will be tabulated including the number of subjects who completed the study as well as the reason for discontinuation for non-completers. The number of subjects in each of the analysis populations, the duration of time on study, and the number of injections will also be displayed. The number and type of protocol violations will be summarized.

8.2.3 *Safety Endpoints*

AEs will be coded using MedDRA and will be presented by System/Organ/Class and preferred term. Some AEs will be categorized and summarized by Grade as defined in CTCAE v 3.0. Concomitant medications will be coded using the CTCAE v 4.0 and summarized by drug class and generic name.

Tables and graphs will show changes from baseline through one year in:

- Physical examination
- Vital signs
- Safety labs, including hematology and serum chemistry

Other safety data that will be presented include:

- DLT
- Adverse events along with their severity and potential relationship to study treatment
- Injection site reactions
- Concomitant medications
- Prophylaxis treatment

8.2.4 ***Efficacy Endpoints***

- Tumor response, time to tumor progression using RECIST, irRECIST or PCWG2 as appropriate
- Survival of subjects at timepoints up to 24 months
- PFS of subjects at timepoints up to 24 months
- [REDACTED]

[REDACTED]

Duration of response will be measured from the time the measurement criteria are met for irCR/irPR (whichever is first recorded) until the first date that progressive disease or death is objectively documented. Subjects who do not relapse will be censored at the day of their last tumor assessment.

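### Response rate, disease control rate and the efficacy set use three incompatible bases, and the disease control denominator is not defined in the visible text

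*Combined protocol and SAP*

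**What the plan says.** Section 8.2.4 (Efficacy Endpoints) defines two rates in consecutive sentences. The first: "Tumor response rate is the total number of CRs plus PRs divided by the number of treated subjects". The second sentence gives this numerator: "Disease control rate is the number of subjects who have CR+PR+SD for a minimum of 12 weeks following the first day of treatment". Its denominator is not the one used for response rate; the count is instead "divided by the number of response-evaluable subjects". No reason is given for the change of denominator. The visible text does not use or define the second term anywhere else. A redacted block follows the sentence.

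Section 8.2.1 (Analysis Sets) defines two sets. The safety population needs at least one dose of either agent, which is the nearest defined set to treated subjects. For efficacy, the rule is: "All subjects who complete at least one cycle of study treatment will be included in the efficacy analyses". A cycle is 12 weeks (Sections 5.2.2 and 6).

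Three other provisions bear on the point:

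- The first on-treatment scan is at Week 10, with a window of one week either side (Section 7.1.5.2).
- Section 5.10 states: "Subjects will not be replaced".
- Section 8.1 plans no inferential analysis. Section 3.2 nevertheless wants the activity results to inform the design of a later randomized Phase 2 trial.

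**The concern.** Two rates that will be read side by side are built on different populations, and a third rule in 8.2.1 fits neither. An analyst working from the visible text cannot tell which subjects belong under the DCR. In an open-label trial that choice could be made after the outcomes are known.

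On the usual meaning of response-evaluable (at least one post-baseline assessment), membership depends on staying in the trial until a scan. No scan is scheduled before about Week 9, and subjects can leave before then through death, clinical progression or withdrawal. Such a subject has not been shown to have 12 weeks of disease control, yet would be removed from the rate and not counted against it. Section 8.2.4 treats a comparable subject differently for time to progression, where a death without reported progression counts as progression on the day of death.

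At stake is the accuracy of a descriptive activity estimate that may feed into planning of the next trial. No hypothesis test or stated decision rule depends on it.

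**Working it through.** The documents state no response rate or DCR, so there is no figure to reproduce. The check compares the three bases and then works out the effect of the denominator.

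**Step 1: the three bases side by side.** Take response-evaluable to mean at least one post-baseline scan (an assumption), and take a completed cycle to mean 12 weeks on study treatment (also an assumption).

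| Illustrative subject | Treated (8.2.4, response rate) | Response-evaluable (8.2.4, DCR) | At least one cycle (8.2.1) |
|---|---|---|---|
| Dies in Week 5, no scan | in | out | out |
| Week 10 scan shows progression, treatment stops before Week 12 | in | in | out |
| Stops in Week 5 without progression, scanned later in follow-up | in | in | out |
| Completes 12 weeks with a scan | in | in | in |

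The three sets differ in membership, so 8.2.1 and the two sentences of 8.2.4 cannot all govern.

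**Step 2: effect on DCR.** Inputs:

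- N = 30 treated, for illustration. Section 2.1.2 plans up to 30 subjects at the selected combination dose.
- C = 12 with disease control (assumed; 9 and 15 are also shown).
- k = treated subjects without a post-baseline scan (assumed: 1, 3, 6 or 9).

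An unscanned subject cannot be in the numerator, so C is the same on both bases:

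- DCR over treated = C/N
- DCR over evaluable = C/(N−k)
- Ratio = N/(N−k), which is 1 if k = 0 and above 1 otherwise

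| k | N/(N−k) | C = 9 (30.0% of treated) | C = 12 (40.0% of treated) | C = 15 (50.0% of treated) |
|---|---|---|---|---|
| 1 | 30/29 = 1.034 | 31.0% | 41.4% | 51.7% |
| 3 | 30/27 = 1.111 | 33.3% | 44.4% | 55.6% |
| 6 | 30/24 = 1.250 | 37.5% | 50.0% | 62.5% |
| 9 | 30/21 = 1.429 | 42.9% | 57.1% | 71.4% |

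**Step 3: effect of the one-cycle set on response rate.** If 8.2.1 overrode the treated denominator, the response rate would move too. With 6 responders and 6 subjects short of one cycle (both assumed), 6/30 = 20.0% becomes 6/24 = 25.0%. Correcting the DCR sentence alone would therefore leave a conflict in place.

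**The case against.** The strongest reply is that inflation is not demonstrated, because the term is undefined. Response-evaluable could instead mean disease assessable at baseline. Section 5.1.2 admits subjects on PSA progression or bone progression alone, and Section 7.1.2.6.1 classes bone lesions as non-measurable. Under that meaning exclusion is fixed at baseline, does not depend on reaching a scan, and has no set direction of bias. This stands: the overstatement is conditional on the post-baseline-scan meaning. A definition in the redacted block also cannot be ruled out, although the two different denominators are visible either way.

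It can also be said that if the one-cycle set governs both rates, an early loss drops out of both, and the contrast between them disappears. That is possible, but it contradicts the denominator that 8.2.4 gives for response rate. It supports reconciling the sections.

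A reader might infer that the unscanned subjects would mainly be toxicity drop-outs or other treatment failures. The documents do not support this. They give no breakdown of early losses, and Sections 5.9 and 7.1.5.3 continue imaging every 12 weeks for subjects who stop for reasons other than progression, so a subject who stops for toxicity may well be scanned.

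A reader might also infer that, on a common denominator, DCR minus response rate would be the stable-disease rate. It need not be. Only DCR carries a 12-week condition, and the first scan usually falls before Week 12. A responder at Week 10 whose response is not shown to last to Week 12 counts in one rate and not in the other.

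Finally, the endpoint is descriptive, and Section 8.2.2 will display the size of each analysis population and tabulate reasons for discontinuation. That limits the harm but does not say which denominator to use.

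**Conclusion.** The visible text applies three incompatible bases to these rates, and one of them is undefined. That much rests on the documents alone.

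The overstatement of DCR by N/(N−k) holds if response-evaluable means having a post-baseline scan and if at least one treated subject leaves unscanned. On that reading the shift is never downward. With 30 treated and 12 controlled it runs from 1.4 percentage points (one subject unscanned) to 17.1 points (nine unscanned). The documents give neither k nor the number controlled, so the range is illustrative, and nothing in them shows that its upper end is likely.

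The consequence is confined to descriptive estimates of activity. It is worth correcting because those estimates are meant to inform a later trial and the correction is cheap.

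**What to change.** 1. In 8.2.4, divide both tumor response rate and DCR by all treated subjects in the relevant Part. Count subjects without a qualifying assessment as non-responders for the first and as not controlled for the second.
2. In 8.2.1, state that the set of subjects completing one cycle does not govern these two rates.
3. Define response-evaluable in 8.2.1 (for example, at least one post-baseline tumor assessment) and report a rate on that set only as a labelled sensitivity analysis.

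The change uses data already collected and needs no new procedures. It costs a few sentences of text and, if any treated subject goes unscanned, a less favourable DCR than a scan-based denominator would give.
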